4.5.1 Study Product Storage

The temperature of the storage unit must be manually recorded daily (excluding non-business days and holidays, as applicable) and continuously monitored and recorded during the course of this clinical trial per site-specific SOPs, and documentation will be maintained. If the temperature fluctuates outside of the required range, the affected study product(s) must be quarantined at the correct storage temperature and labeled as 'Do Not Use' (until further notice). The participating site's research pharmacist must alert the participating site PI and study coordinator, if the temperature fluctuates outside of the required range. In the event the temperature fluctuates outside of the required range, including accidental deep-freezing or disruption of the cold chain, the affected study product(s) must not be administered. The participating site PI or responsible person should immediately contact the DMID Product Support Team at [contact] for further instructions before any additional vaccinations are administered. Based on the information collected, DMID and/or the manufacturer will determine whether the affected study product(s) can be used. If it cannot be used, the participating site will receive specific instructions on how to return the affected study product(s) to the DMID CMS or destroy it on-site. Additional instructions for quarantine and DMID contact information are provided in the protocol-specific MOP.

All study products (except Normal Saline) should be maintained in controlled-access storage at -60°C or colder. The freezer should have an automated temperature recording and alert system. There must be an available back up freezer. The freezers must be connected to a back-up generator, or alternate plan in the event of a power failure. The pharmacy must have in place a

24-hour alert system that allows for rapid response in case of freezer malfunctioning. In addition, vaccine accountability study staff (e.g., pharmacy staff) are required to keep a temperature log to establish a record of compliance with these storage conditions. Only vaccine accountability study staff (e.g., pharmacy staff) should have access to the product used in this study. The participating site is responsible for reporting any study product that was not temperature controlled during shipment or during storage to the pharmacy staff. Such study product will be retained for inspection by the pharmacy staff and disposed of according to approved methods.

5 SELECTION OF SUBJECTS AND STUDY ENROLLMENT AND WITHDRAWAL/DISCONTINUATION

Up to 135 men and non-pregnant women (17 for Stage 1 and up to 118 for Stage 2), aged 18 or older, who are in good health and meet all eligibility criteria will be enrolled at IDCRC sites participating in this trial. The target population should reflect the community at large at each of the participating IDCRC sites.

For Stages 1 and 2, recruitment of eligible participants will proceed if the candidate participant expresses no intention to seek an EUA/licensed COVID-19 vaccine at least until completion of the key follow-up timepoint (at least 1 month after the last study vaccination). The study investigator or staff will discuss with potential participants that de-identified antibody aggregate data will be shared with them during the conduct of the study. It will be explained to potential study participants that, in the absence of a clear immune correlate of protection, the aggregate data could be used to estimate how each study group is responding to the study products.

Subject Inclusion and Exclusion Criteria must be confirmed by a study clinician licensed to make medical diagnoses and listed on the Form FDA 1572 as the site PI or sub-investigator.

No exemptions are granted on Subject Inclusion/Exclusion Criteria in DMID-sponsored studies. Questions about eligibility will be directed toward the DMID Medical Officer.

Healthy adults will be recruited through IRB-approved advertising and screened through the participating institution's screening protocol to confirm eligibility requirements for participation. The following eligibility criteria will be used:

5.1 Eligibility Criteria

5.1.1 Subject Inclusion Criteria

Subjects eligible to participate in this trial must meet all of the following inclusion criteria:

1. Provide written informed consent prior to initiation of any study procedures.
2. Able and willing (in the investigator's opinion) to comply with all study requirements.
3. Are men or non-pregnant women aged 18 years or older at enrollment.
4. Are in good health*.

As defined by absence of clinically significant medical conditions defined by the CDC as increasing risk for severe COVID-19 disease (see exclusion criteria), or other acute or chronic medical conditions determined by medical history, physical examination (PE), screening laboratory test results, and/or clinical assessment of the investigator that are either listed as exclusion criteria below or in the opinion of the investigator would increase risk for study participation or affect the assessment of the safety of subjects. Chronic medical conditions should be stable for the last 60 days (no hospitalizations, emergency room or urgent care for condition, or invasive medical procedures). Any prescription change that is due to change of health care provider, insurance company, etc., or done for financial reasons, and in the same class of medication, will not be considered a deviation of this inclusion criterion. Any change in prescription medication due to **improvement of a disease outcome, as determined by the participating site PI or appropriate sub- investigator, will not be considered a deviation of this inclusion criterion. Subjects may be on chronic or as needed (prn) medications if, in the opinion of the participating site PI or appropriate sub-investigator, they pose no additional risk to subject safety or assessment of reactogenicity and immunogenicity, and do not indicate a worsening of medical diagnosis/condition. Similarly, medication changes in the 60 days prior to enrollment as well as subsequent to enrollment and study vaccination are acceptable provided the change was not precipitated by deterioration in the chronic medical condition, and there is no anticipated additional risk to the subject or interference with the evaluation of responses to study vaccination.*

5. Agree to refrain from blood donation during the course of the study.
6. Plan to remain living in the area for the duration of the study.
7. Women of childbearing potential (WOCBP)* must plan to avoid pregnancy for at least 60 days after the last study vaccination and be willing to use an adequate method of contraception** consistently for 30 days prior to first study vaccine and for at least 60 days after the last study vaccine.

**Not sterilized via bilateral oophorectomy, tubal ligation/salpingectomy, hysterectomy, or successful Essure® placement (permanent, non-surgical, non-hormonal sterilization with documented radiological confirmation test at least 90 days after the procedure); still menstruating; or < 1 year has passed since the last menses if menopausal.*

***Acceptable methods of birth control include the following: oral contraceptives, injection hormonal contraceptive, implant hormonal contraceptive, hormonal patch, intrauterine device, spermicidal products and barrier methods (such as cervical sponge,*

diaphragm, or condom with spermicide), abstinence, monogamous with a vasectomized partner, non-male sexual relationship.

8. Women of childbearing potential must have a negative urine or serum pregnancy test within 24 hours prior to each study vaccination.
9. Vital signs within acceptable ranges:
 - Pulse >50 and ≤ 100 beats per minute
 - Systolic blood pressure (BP) ≤ 140 millimeters of mercury (mmHg)
 - Diastolic BP ≤ 90 mmHg
 - Oral temperature $<37.8^{\circ}\text{C}$ (100.0°F)
10. Clinical screening lab evaluations (white blood cell (WBC), hemoglobin (HgB), platelets (PLT), alanine aminotransferase (ALT), aspartate aminotransferase (AST), alkaline phosphatase (ALP), total bilirubin (T Bili), creatine kinase (CK), serum creatinine (Cr) and prothrombin time (PT)/partial thromboplastin time (PTT)) are within acceptable normal reference ranges at the clinical lab being used*.

**With the exception that ALT, AST, ALP, and creatinine values that are below the reference range will not be exclusionary as these values below reference range are clinically insignificant. Any other screening lab value outside the reference range that is thought to be clinically insignificant by a site investigator must be discussed with the DMID Medical Officer prior to enrollment.*

11. Must agree to genetic testing and storage of samples for secondary research.
12. Received at least 2 doses of EUA/licensed mRNA vaccines or at least 1 dose of Ad26 vaccine followed by an mRNA booster, with the last COVID-19 vaccine dose given at least 112 days prior to enrollment (Stage 2 only), as confirmed via CDC vaccination card or other appropriate documentation. Subjects may or may not have been previously infected with SARS-CoV-2.*

**In version 7.0 of the protocol, we prioritize enrollments of subjects who have either received 3 EUA/licensed mRNA vaccinations (SAM-S-TCE single boosting Groups 7A, 7B, 10A, 10B, 11A, 11B, 12A and 12B, and ChAd-S-TCE single boosting Groups 13-15) or 1-2 doses of EUA/licensed Ad26 prior to 1 dose of EUA/licensed mRNA (SAM-S-TCE double boosting Groups 8A, 8B, 12A and 12B).*

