		3B	7	30 µg SAM-S/ 3 µg SAM-S	84-129
		4	3	10 µg SAM-S-TCE/ 3 µg SAM-S-TCE	84-129
2**	SAM-S-TCE Boosts after EUA/licensed mRNA (Groups 5-7) and Ad26 (Group 8) COVID-19 Vaccines (18-60 yo)	5	10	3 µg SAM-S-TCE	≥112
		6	10	6 µg SAM-S-TCE	≥112
		7A&B [#] ****	8-12	10 µg SAM-S-TCE	≥112
		8A&B [#] ****	8-12	10 µg SAM-S-TCE/ 10 µg SAM-S-TCE***	≥112/ 56***
		9	8	3 µg SAM-S-TCE	≥112
	SAM-S-TCE Boosts after approved/licensed mRNA (Groups 9-11) and Ad26 (Group 12) COVID-19 Vaccines (>60 yo)	10A&B [#]	8-12	6 µg SAM-S-TCE	≥112
		11A&B [#]	8-12	10 µg SAM-S-TCE	≥112
		12A&B [#]	8-12	10 µg SAM-S-TCE/ 10 µg SAM-S-TCE***	≥112/ 56***
		13	7-10	5 x 10 ¹⁰ vp ChAd-S-TCE	≥112
	ChAd-S-TCE Boosts after approved/licensed mRNA COVID-19 Vaccines (>60 yo)	14	7-10	1 x 10 ¹¹ vp ChAd-S-TCE	≥112
		15	7-10	5 x 10 ¹¹ vp ChAd-S-TCE	≥112

[figure not shown]
*Were enrolled prior to protocol version 5.0. No further enrollment will occur in Stage 1. Group 1A, as noted in protocol version 4.0, is noted above as Group 1. Groups 1B and 2, as noted in protocol version 4.0, have been eliminated, due to anticipated challenges with enrollment of naïve subjects.

**Will be enrolled under protocol versions 5.0 and later; Stage 2 was redesigned in version 5.0 to focus on subjects previously given primary vaccination series of mRNA or Ad26 COVID-19 vaccines and has now been redesigned to also include those given recommended COVID-19 booster vaccinations. All Stage 2 subjects will receive single or double boosts of SAM-S-TCE or a single boost with ChAd-S-TCE. Groups 5, 6, 8, 9, 10, 12, and 13-15 are dose escalations with 3 sentinels/group (irrespective of subgroup) who will be followed for 72 hours post vaccination. After all 3 sentinels are evaluated for 72 hours and no safety issues are observed, the remainder of the group will be enrolled and followed through Day 8 after study vaccination before dose escalation. Dosing in Groups 7 and 11 (10 µg SAM-S-TCE) will proceed with 3 sentinels/group (irrespective of subgroup) monitored for 7 days post vaccination prior to enrollment of the remainder of the group; enrollment into Group 7 will depend on all safety data from Group 11 generated through 28 days of follow up post-vaccination.

***Will administer the highest tolerable dose as determined by the dose escalations. For the SAM-S-TCE double boosting groups, the interval after the last EUA/licensed COVID-19 vaccination will be ≥ 112 days and the interval between the 2 SAM-S-TCE boosts will be 56 days.

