3 STUDY DESIGN, OBJECTIVES AND ENDPOINTS OR OUTCOME MEASURES

3.1 Study Design Description

This is a multicenter, US-only, phase 1, open-label, dose escalation, non-randomized study of the safety, tolerability, and immunogenicity of investigational ChAd and SAM SARS-CoV-2 vaccines in healthy adult subjects. Homologous and heterologous prime-boost vaccination schedules (Stage 1), as well as boost(s) after receipt of EUA/licensed COVID-19 vaccines (Stage 2) will be examined. Subjects' willingness to receive ChAd vaccines will be assessed and documented at the time of informed consent and considered to determine group assignments.

This phase 1 study will enroll 17 Stage 1 and up to 118 Stage 2 subjects. Eligible subjects will be enrolled in different groups based on their age (18-60 years old and >60 years old) and their EUA/licensed COVID-19 vaccination status. A sentinel approach with 72-hour (Stage 1, and Stage 2, Groups 5, 6, 8*-10, 12, 13-15) or 7-day observation times (Groups 7* and 11) will be used, before recruiting the remainder of each dose escalation group. Decisions about dose escalation will be determined by the SSC with consultation with the DSMB as needed after all subjects in each group have been observed through Day 8 post first study vaccination. All subjects will be followed through 12 months after their last study vaccination. Vaccinated subjects will be carefully monitored for exposure and infection to SARS-CoV-2 throughout the study.

Escalation to the highest dose (10 µg) of SAM-S-TCE in younger subjects will proceed only following safety assessments of the 10 µg dose in older subjects for a period of 28 days post-vaccination.

In addition, the dosage of SAM-S-TCE given as a double boost to subjects previously vaccinated with the Johnson & Johnson/Janssen Ad26 COVID-19 EUA vaccine in Groups 8A, 8B, and 12A, 12B will be determined based on the dose escalation reactogenicity and immunogenicity results in Groups 5-7 and 9-11, respectively.

See [Table 1](#), [Figure 1](#), [Table 3](#), and [Section 10](#) for details on group assignments and study vaccines and doses to be administered.

* After protocol version 9.0 was implemented, it was decided not to enroll subjects into Groups 7 and 8 because of competing priorities and predicted difficulties enrolling into these two groups.

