10.3 Treatment Assignment Procedures

10.3.1 Group Assignment Procedures

Prior to version 3.0 of the protocol, subjects 18-60 years old were randomized in a 1:1 ratio to Groups 1 and 3A. After protocol version 3.0, no random assignment to groups is planned or will be conducted. As of the writing of protocol version 5.0, Groups 1, 3A, 3B and 4 will not enroll any additional subjects, and no further enrollments are planned for Stage 1. After protocol version 9.0 was implemented, it was decided Groups 7A, 7B, 8A and 8B in Stage 2 will not be opened to enroll subjects.

Subjects enrolled into Stage 2 may elect not to receive ChAd-S-TCE, in which case the subject will only be considered for enrollment into SAM-S-TCE single or double boosted vaccination groups. Subjects that consent to receiving a ChAd vaccine may enroll into groups that do not provide ChAd vaccine, but enrollment into groups providing a ChAd vaccine will be prioritized.

As of the writing of protocol version 5.0, subjects will be enrolled into the different groups according to 1) age (see [Table 1](#)), 2) whether the subject consented to ChAd vaccine, and 3) dose escalation dependencies (as specified in [Section 8.1.6](#)). In protocol version 8.0 Stage 2 Groups 7-8 and 10-12 will enroll 8-12 subjects that are vaccinated, with either no prior infection history or evidence of infection at least 4 months previously into A & B subgroups, respectively. Groups 13-15 will allow sample sizes of 7-10 subjects total with no prespecified ratio for infected vs noninfected.

See [Figure 1](#). Stage 1 does not need to be completed prior to enrollment of subjects in Stage 2.

If replacements are needed, each replacement subject will receive the same treatment as the originally enrolled subject.

Treatment allocation schedules will be generated by a statistician at Emmes, the statistical and data coordinating center (SDCC) for this study. Subjects will be registered using a web-based application developed by Emmes.

After informed consent has been obtained and study eligibility has been established at the Screening Visit, subjects will return to the clinical site for their Enrollment Visit, when the first dose of study product will be administered (see [Section 6.2](#)). Group assignment will occur following confirmation of their eligibility and their willingness to participate.

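### The inclusion 12 footnote places Group 12 under two populations and two boosting regimens, and neither the 10.3.1 assignment list nor any numbered criterion ties the group to Ad26 priming

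*Protocol*

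**What the plan says.** **Eligibility.** The body of inclusion 12 (5.1.1) asks of Stage 2 subjects: "Received at least 2 doses of EUA/licensed mRNA vaccines or at least 1 dose of Ad26 vaccine followed by an mRNA booster". It does not say which history belongs to which group. Its footnote, dated to protocol version 7.0, sets enrolment priorities:

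- Recipients of three mRNA doses: "SAM-S-TCE single boosting Groups 7A, 7B, 10A, 10B, 11A, 11B, 12A and 12B, and ChAd-S-TCE single boosting Groups 13-15".
- Recipients of one or two Ad26 doses and then one mRNA dose: "SAM-S-TCE double boosting Groups 8A, 8B, 12A and 12B".

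The footnote to exclusion 7 (5.1.3) permits prior Ad26 vaccine in Groups 8 and 12. It is worded as a permission.

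**Definition of Group 12 elsewhere.** Table 1 heads the older SAM-S-TCE rows "mRNA (Groups 9-11) and Ad26 (Group 12) COVID-19 Vaccines (>60 yo" and gives Group 12 two doses 56 days apart. Section 3.1 describes the dosage "given as a double boost to subjects previously vaccinated with the Johnson & Johnson/Janssen Ad26 COVID-19 EUA vaccine in Groups 8A, 8B, and 12A, 12B". Section 8.1.6 describes Group 12 as double boosting after at least one Ad26 dose and one mRNA booster. Section 2.2.4 gives mRNA-vaccinated subjects one boost and Ad26-then-mRNA subjects two. Table 3 doses 12A and 12B on D1 and D57.

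**Assignment.** Section 3.1 says subjects are grouped "based on their age (18-60 years old and >60 years old) and their EUA/licensed COVID-19 vaccination status". Section 10.3.1 lists age first, then "2) whether the subject consented to ChAd vaccine, and 3) dose escalation dependencies". It later adds infection history for the A and B subgroups.

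**Closed groups.** The notes to Table 1 and Section 3.1 say Groups 7 and 8 will not be enrolled.

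**The concern.** One group cannot be both a single-boost group for subjects given three mRNA doses and a double-boost group for subjects primed with Ad26. The conflict sits inside a numbered eligibility criterion, and Section 5 allows no exemptions from the criteria, so sites depend on their wording.

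The assignment text does not correct it. Section 3.1 sends the reader to Section 10 for details of group assignment, and there the prior-vaccine factor is missing. According to 10.3.1, the registration module assigns a subject once demographic and eligibility data are entered, so a factor absent from the list may also be absent from the check.

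The primary objective in Table 2 covers adults previously given an mRNA or an adenoviral-vectored COVID-19 vaccine. With Group 8 not opened, the adenoviral part rests on Group 12, planned at 8-12 subjects. It is also the only Stage 2 group still receiving two boosts.

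**Working it through.** **Step 1: the passages side by side.**

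| Place | Population for Group 12 | Boosts |
|---|---|---|
| Inclusion 12 footnote, first list | three mRNA doses | single |
| Inclusion 12 footnote, second list | Ad26, then mRNA | double |
| Table 1 | Ad26 | double |
| 3.1 | Ad26 | double |
| 8.1.6 | Ad26 plus mRNA booster | double |
| 2.2.4 (group not named) | Ad26 plus mRNA booster, for the two-boost regimen | double |
| Table 3 | not stated | D1 and D57 |

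Only the first list in the footnote disagrees.

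**Step 2: does any rule exclude an mRNA-only subject over 60 from Group 12?**

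- Inclusion 12, body: met by two or more mRNA doses.
- Exclusion 7: keeps Ad26 recipients out of groups other than 8 and 12. It does not bar mRNA-only recipients from 12.
- 10.3.1: age, ChAd consent and escalation dependencies; Table 1 is cited for age only.
- 3.1: vaccination status is a stated basis for grouping. Read with Table 1, this does exclude such a subject.

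So the exclusion follows from the design description, not from the numbered criteria or the assignment list.

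**Step 3: the plan's own precision figures.** For a group of 12 at a true event rate of 20%, Section 10.2 and Table 4 give 93.1% for at least one event:

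1 − 0.8^12 = 1 − 0.0687 = 0.931, which reproduces it.

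In Table 5, with SD 1.0 on the log_e scale, n = 12 and an observed titer of 100, the upper limit is 188.8, a factor of 1.89. The formula exp(t(0.975, n−1) × SD / √n) gives exp(2.201 × 1.0 / √12) = 1.89, which reproduces it.

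**Step 4: illustration.** The protocol gives no mix, so the number of Ad26-primed subjects out of 12 is assumed.

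| Ad26-primed of 12 | P(at least 1 event at 20%) = 1 − 0.8^n | 95% CI factor for the GMT, SD 1.0 |
|---|---|---|
| 12 | 93.1% | 1.89 |
| 8 | 83.2% | 2.31 |
| 6 | 73.8% | 2.86 |
| 4 | 59.0% | 4.91 |

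If Group 12 closes at its lower size of 8 and half are Ad26-primed, the same formulas take the figures from 83.2% to 59.0% and from 2.31 to 4.91.

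**The case against.** The strongest reply is that the protocol read as a whole is clear. Section 3.1 groups subjects by vaccination status as well as age. Three places define Group 12 as Ad26-primed and double-boosted, and the rationale in 2.2.4 and the schedule in Table 3 agree with them. The footnote states a priority as of version 7.0 and does not set eligibility, so the first mention of 12A and 12B is most plausibly a drafting slip. All of this stands, and it makes large-scale misenrolment unlikely.

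A reader might infer more than the documents support, in three ways:

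- **That assignment ignores prior vaccine type, so Group 12 can simply be filled with mRNA-primed subjects.** The omission is real in 10.3.1 but not in the protocol as a whole, because 3.1 names the factor and enrolling such subjects would contradict Table 1 and 8.1.6.
- **That the adenoviral-primed population would be left with no estimate.** A partial mix leaves fewer subjects and a less precise estimate.
- **That mixing would confound Group 11 against Group 12.** Those groups already differ by design in priming vaccine and in number of boosts, and 10.1 plans no hypothesis test between groups.

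The reply does not remove the double listing, the difference between 3.1 and 10.3.1, or the absence of a numbered criterion requiring Ad26 priming for Group 12.

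**Conclusion.** The point holds as an internal contradiction in the eligibility and assignment text: the footnote conflicts with Table 1, 3.1 and 8.1.6 on who enters Group 12 and how many boosts they receive, and 10.3.1 drops a factor that 3.1 states. It deserves correction because it concerns the only Ad26-primed Stage 2 cohort left, of at most 12 subjects, where every misplaced subject costs information on part of the primary objective.

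The size depends on how many mRNA-primed subjects would enter, which the documents do not give. The figures for 8, 6 and 4 of 12 are illustrations under that assumption, and the GMT factors also assume SD 1.0, the larger of the two values in Table 5. With correct enrolment of 12 Ad26-primed subjects nothing is lost.

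**What to change.** 1. Reconcile the inclusion 12 footnote with Table 1, 2.2.4, 3.1 and 8.1.6 so that Groups 12A and 12B appear under one population and one regimen. Which population and regimen is for the sponsor to confirm.
2. Add the vaccination-status factor of 3.1 to the assignment list in 10.3.1, stated as prior primary vaccine type (mRNA, or Ad26 followed by mRNA).
3. Build the same factor into the registration-module check for Group 12.

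The cost is two wording edits and one edit check. The possible downside is slower enrolment into Group 12 if sites have been applying the broader reading.
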